## 5. Sample size

The sample size was calculated according to Sikora et al. [31] who compared the efficacy of PBM to a placebo group (laser off). In that study, the mean and standard deviation (SD) of the VAS score in the placebo group at the end of treatment was  $2.417 \pm 2.918$ . Considering that acceptable improvement in the PBM group would be at least 10% after the intervention, we obtained an effect value ( $E$ ) = 2.17. The sample size was then calculated using a t-test for comparing the means of continuous variables, whose standardized effect size was 0.70 assuming a one-sided alpha error of 0.05 and a beta error of 0.20, resulting in 28 patients divided into two intervention groups.

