### 2. Participants

Patients older than 18 years who had a burning or dysesthetic sensation in the oral mucosa that recurred daily for more than 2 hours per day for more than 3 months, in the absence of clinically evident causal lesions [4], were included in the study. We also included patients with hyposalivation or any systemic alteration that could be related to a burning sensation in the oral mucosa but who did not have clinical alterations in the oral mucosa such as erosive lichen planus, geographic tongue, infections, allergic reactions, trauma, or injuries caused by physical or chemical agents. Patients who did not comply with the treatment protocol of the study were excluded from the sample.

Before the beginning of treatment, clinical and sociodemographic data of the patients were collected and blood tests were requested (complete blood count, fasting blood glucose, total cholesterol and fractions, triglycerides, ferritin, vitamin B12, folic acid, zinc, thyroxine, triiodothyronine, and antinuclear antibodies).

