#### 4. Outcomes

Pain/burning was the primary outcome and was measured on a visual analogue scale (VAS; 0-10 cm). The patients were asked to choose a number from 0 to 10 on the scale to describe the level of intensity of their symptoms.

Changes in unstimulated salivary flow, xerostomia, and dysgeusia were the secondary outcomes. Saliva was collected as described by Navazesh and Kumar [26] and patients with an unstimulated salivary flow rate  $< 0.1$  ml/min were classified as having hyposalivation.

Information on xerostomia was collected according to the method of Murray Thomson et al. (2006) using a standard question and the Xerostomia Inventory (XI). Patients answered the following question: "How often does your mouth feel dry?" (response options: "never", "occasionally", "frequently", "always"). On each occasion, those who gave either of the latter two responses were categorised as xerostomic. The XI was used to obtain information on the severity of xerostomia symptoms, being an 11-item summated rating scale which combines the responses to 11 individual items into a single continuous scale score which represents the severity of chronic xerostomia, and higher scores represent more severe symptoms. The patients were asked to choose one of five responses ("never", scoring 1; "hardly ever", 2; "occasionally", 3; "fairly often", 4 and "very often", 5) to the following statements referring to the previous 4 weeks: "my mouth feels dry"; "my lips feel dry"; "I get up at night to drink"; "my mouth feels dry when eating a meal"; "I sip liquids to aid in swallowing food"; "I suck sweets or cough lollies to relieve dry mouth"; "my throat feels dry"; "the skin of my face feels dry"; "my eyes feel dry"; "my lips feel dry" and "the inside of my nose feels dry". Each individual's responses were scored and summed to give a single XI score.

Dysgeusia was analyzed using an adaptation of the method proposed by Muller et al. [28], in which the four basic tastes at four different concentrations are tested. Urea was used as bitter taste as proposed by Henn et al. [29] (sucrose solution: 0.4 g/mL, 0.2 g/mL, 0.1 g/mL, 0.005 g/mL; sodium chloride: 0.25 g/mL, 0.1 g/mL, 0.04 g/mL, 0.016 g/mL; citric acid: 0.3 g/mL, 0.165 g/mL, 0.09 g/mL, 0.05 g/mL; urea: 0.005 g/mL, 0.04 g/mL, 0.02 g/mL, 0.01 g/mL). Filter paper strips were impregnated with the test solutions as proposed by Kettenmann et al.

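### Section 5 sizes the trial on an effect that cannot coexist with its own VAS mean and SD on a 0–10 scale; target, direction and SD need restating

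*Combined protocol and SAP*

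**What the plan says.** All references are to the combined protocol and SAP.

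- **Section 4 (Outcomes).** The primary outcome is pain/burning on a VAS: "The patients were asked to choose a number from 0 to 10 on the scale". Zero is the lowest possible value.
- **Section 5 (Sample size).** The only VAS level and spread given come from the laser-off arm of a cited PBM study: "the mean and standard deviation (SD) of the VAS score in the placebo group at the end of treatment was $2.417 \pm 2.918". The plan then assumes that "acceptable improvement in the PBM group would be at least 10% after the intervention", and continues "we obtained an effect value ( $E$ ) = 2.17". The calculation is a t-test for two means "whose standardized effect size was 0.70", "assuming a one-sided alpha error of 0.05 and a beta error of 0.20". The result is 28 patients across two groups.
- **Section 3 (Interventions).** PBM is the control treatment and TENS the study treatment.
- **Section 2 (Participants).** Burning must have "recurred daily for more than 2 hours per day for more than 3 months". No minimum VAS score is required.

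The plan gives no expected baseline VAS, no expected TENS mean, no TENS–PBM difference in VAS points, and no direction for the one-sided test.

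**The concern.** A sample size rests on a comparator mean, a difference and an SD that must all be possible on the instrument used. Here the comparator is expected at a little over 2 on a scale that ends at 0, while the effect used for sizing is also a little over 2. A TENS advantage of that size would leave the TENS arm almost entirely without symptoms, and an arm with nearly all scores at 0 cannot have an SD close to 3.

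Two things are at stake. First, the planning statement does not describe a result the trial could observe, so its 80% power claim has no clear meaning. Second, if the enrolled patients do score as low as the planning figures suggest, there is little room to record improvement. A non-significant comparison of about 14 patients per arm could then reflect lack of room on the scale as much as equal treatments.

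**Working it through.** **Inputs.** Scale 0–10 (section 4). Mean 2.417, SD 2.918, improvement of at least 10%, E = 2.17, d = 0.70, one-sided alpha 0.05, power 0.80, total 28 (all section 5). Assumption: equal allocation, so 14 per arm; no ratio is stated.

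**1. The plan's own figure.** Two-sample comparison, n per arm = 2(1.645 + 0.842)²/0.70² = 25.2, so 26. The exact t-test gives 25.94, also 26. That is 52 in total, so 28 is not reproduced. It is close to 2 × 14, where 14.07 is the n for a one-sample or paired t-test. With 14 per arm and d = 0.70, the exact one-sided t-test has power of about 56%. This shortfall is a separate matter, but 56% is the reference for step 5.

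**2. Where E comes from.** 0.9 × 2.417 = 2.175. E = 2.17 therefore matches the expected PBM mean. The 10% improvement itself is 0.1 × 2.417 = 0.24 points. E and d also do not share the stated SD: 2.17/2.918 = 0.74, and 2.17/0.70 = 3.10. With SD 2.918, d = 0.70 is 0.70 × 2.918 = 2.04 points.

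**3. Implied TENS mean and largest possible SD.** On a 0–10 scale with mean m, the SD cannot exceed √(m(10 − m)).

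| Comparator mean | Effect | TENS mean | Share of distance to 0 | Largest SD |
|---|---|---|---|---|
| 2.175 | 2.04 | 0.13 | 94% | 1.14 |
| 2.175 | 2.17 | 0.005 | 99.8% | 0.22 |
| 2.417 | 2.04 | 0.37 | 85% | 1.90 |
| 2.417 | 2.17 | 0.25 | 90% | 1.55 |

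Every ceiling is below 2.918. This step needs no assumption about the shape of the distribution.

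**4. The literal 10%.** A target of 0.24 points below 2.175 gives a mean of 1.93, where the largest SD is √(1.93 × 8.07) = 3.95. An SD of 2.918 is then possible and the floor does not limit the target. But d = 0.242/2.918 = 0.083, which needs about 1,803 per arm (one-sided 5%, 80% power).

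**5. How much the floor could cost.** Assumptions: beta-shaped comparator scores with SD 2.918; every TENS patient 2.04 points lower, cut off at 0; 14 per arm; single-visit t-test, one-sided 5%.

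| Comparator mean | Patients below 2.04 | Recorded difference | d | Power |
|---|---|---|---|---|
| 2.175 | 66% | 0.94 | 0.36 | 24% |
| 2.417 | 61% | 1.07 | 0.41 | 28% |
| 4 | 33% | 1.65 | 0.61 | 47% |
| 6 | 13% | 1.92 | 0.68 | 54% |
| no floor | – | 2.04 | 0.70 | 56% |

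The documents give no T0 distribution, so the range is shown.

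**The case against.** The strongest reply is that the plan never states a 2-point TENS advantage. Its only stated improvement belongs to PBM, the one-sided test has no declared direction, and 2.04 appears only when 0.70 is multiplied by 2.918. This is fair. It means the incompatibility is tied to how E was formed. A reader might infer that the target would sit at the floor even with E corrected; the documents do not support that, because a literal 10% is far from the floor (step 4). If TENS were worse than PBM, the floor would not limit the gap either. What stands is that E = 2.17 and d = 0.70 are the only effects section 5 offers, and neither fits its mean and SD as a TENS benefit.

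A reader might also infer that a useful TENS advantage can barely be recorded, or that low power here is a floor effect. Neither is established. The 2.2–2.4 level is a post-treatment placebo mean from another study, and patients with daily burning in this trial may score higher. At a mean of 6 the floor takes power only from 56% to 54%; the rest of the gap to 80% comes from having 14 per arm. The truncation model also assumes a constant benefit for everyone, although a patient scoring 1 may have no hidden 2-point benefit to lose, and it replaces the repeated-measures ANOVA of section 8 with a single-visit test. Finally, a TENS arm near 0 would have a smaller SD. If SD scales with the mean, d = 0.70 against 2.417 needs a gap of about 1.5 points (TENS mean about 0.9), which is short of near-complete remission. That weakens any claim of impossibility for d = 0.70 itself, but confirms that the common SD has to be replaced.

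A minimum entry score would narrow a deliberately broad population, and section 1 dates the study April 2021 to February 2022, so it cannot change this enrolment.

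**Conclusion.** The point holds as an internal inconsistency in section 5. Read as a TENS advantage, the sizing effect uses 85% to nearly 100% of the distance from the comparator mean to 0 and implies a TENS mean of about 0.0–0.4. The SD there is at most about 0.2–1.9, against the 2.918 that the plan supplies. This rests only on the plan's figures and the bounds of the scale, plus two readings: that the effect is a TENS benefit over PBM, and that 2.918 is the SD behind d = 0.70 (the E = 2.17 rows do not need the second to give the implied mean).

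The effect on power is much less certain. It ranges from about 24–28% if comparator scores sit at 2.2–2.4 to about 54% at a mean of 6, beside 56% with no floor, all under assumed beta shapes and a constant benefit. The documents do not show which case applies, and no minimum VAS at entry secures the better one. The planning statement should be corrected and floor counts reported; the material does not support a conclusion that the trial could not detect a TENS benefit.

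**What to change.** 1. **Section 5.** State the expected PBM mean, the TENS–PBM target difference in VAS points and its direction, and an SD that can coexist with both means on 0–10 (the check is that each arm's SD stays below √(m(10 − m))). Restate the standardized effect from those figures, and give the power that 28 patients deliver for it, labelled as a recalculation made after the original sizing.
2. **Reporting.** From VAS data already collected under section 4, report by arm the share of patients with low scores at T0 and the share at 0 at T2. If many are at the floor, say so next to the primary result and do not present a non-significant comparison as evidence of no difference.
3. **Future trial only.** A minimum T0 VAS score is an option to weigh against a narrower population; it is not a correction to this one.

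The cost is a few rewritten sentences in section 5, one small descriptive table and no new data. The downside is a less favourable planning statement.

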## STUDY PROTOCOL AND STATISTICAL ANALYSIS PLAN

### 1. Study design

This randomized clinical trial involved patients with burning mouth seen at the Stomatology Service of the Department of Dentistry, Federal University of Rio Grande do Norte (UFRN), Natal-RN, Brazil, from April 2021 to February 2022. The study was approved by the Ethics Committee of UFRN (Approval number 4.066.032) and was conducted in accordance with the Declaration of Helsinki. This clinical trial followed the Consort Statement (<http://www.consort-statement.org>) and was registered at clinicaltrials.gov (Number: NCT05816200).

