### 3. Interventions

In the study group, a portable TENS 7000 device (Roscoe Medical, Middleburg Heights, OH, USA) was used for stimulation. The device was calibrated for a frequency of 50 Hz and its intensity was modulated according to the patient's comfort (pulse amplitude of 1-4). Each session lasted 25 minutes. The self-adhesive electrodes were connected to the channels of the device and **attached to the patient's skin** of both facial sides next of the major salivary glands (parotid and submandibular glands), passing through the mandibular branch of the trigeminal

nerve as shown in figure 1. The patients were submitted to the respective treatment protocol once a week for eight consecutive weeks, totaling 8 treatment sessions.

In the control group, photobiomodulation was applied using a laser whose parameters are represented in table 1. During laser application, the patients and the clinician wore the protective glasses (figure 2).

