## 8. Statistical analysis

All data were analyzed using the Statistical Package for the Social Sciences 25.0 (SPSS). First, the collected data were submitted to descriptive analysis. Fisher's exact test was then used to determine whether statistically significant differences in systemic alterations, psychiatric disorders and medication use exist at T0 between the TENS and PBM groups.

The quantitative data (VAS score and unstimulated salivary flow) were analyzed using the Kolmogorov-Smirnov normality test to assess if the data are normally distributed, which

was confirmed based on the mean error. Two-factor ANOVA was used to analyze intergroup (TENS and PBM) and intragroup (repeated measures at T0, T1, T2 and T3) differences in mean VAS scores and unstimulated salivary flow. For this purpose, the assumptions of sphericity were tested using the Mauchly test. The post-test of intergroup and intragroup interactions was carried out based on Bonferroni corrections, as well as using the trend test of the interaction between time and intervention. A level of statistical significance of 95% was adopted for all tests.

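### In section 5, E = 2.17 does not follow from the stated 10% improvement, and a total of 28 patients does not follow from 0.70 SD

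*Combined protocol and SAP*

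**What the plan says.** Section 5 (Sample size) builds the calculation in four steps.

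- It takes its reference values from an earlier study "who compared the efficacy of PBM to a placebo group (laser off"), where "the mean and standard deviation (SD) of the VAS score in the placebo group at the end of treatment was" 2.417 ± 2.918.
- It then sets a criterion and an effect: "Considering that acceptable improvement in the PBM group would be at least 10% after the intervention, we obtained an effect value" (E) = 2.17.
- It specifies a t-test for two means "whose standardized effect size was 0.70 assuming a one-sided alpha error of 0.05 and a beta error of 0.20".
- It ends with the number of patients: "resulting in 28 patients divided into two intervention groups".

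The section does not say what the 10% is a percentage of, how E was computed, or which SD turns E into 0.70.

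Elsewhere, section 4 gives the outcome scale as 0 to 10. Section 3 makes PBM the comparator: "In the control group, photobiomodulation was applied using a laser". Section 8 analyses the VAS with a different model from the t-test: "Two-factor ANOVA was used to analyze intergroup (TENS and PBM) and intragroup (repeated measures at T0, T1, T2 and T3) differences".

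**The concern.** The sentence presents E as the product of the 10% criterion, and E then appears to lead to the standardised effect of 0.70 that fixes the sample size. If 2.17 is not a 10% improvement, the only rationale given for the size of the trial does not support the effect entered. A reader would take the trial to have been sized to detect a 10% improvement.

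This matters most for a null result. The comparator is an active treatment, so a non-significant TENS versus PBM difference could be read as similar efficacy. If the trial had little power for differences of the order of 10%, that reading would be unsafe.

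The last step of the paragraph, from 0.70 SD to 28 patients, needs its own check, because it can fail whatever the origin of 0.70.

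**Working it through.** **Inputs.** From section 5: mean 2.417, SD 2.918, improvement of at least 10%, E = 2.17, d = 0.70, one-sided alpha 0.05, power 80%, 28 patients. From section 4: scale 0 to 10. Assumption: 14 per group, since no allocation ratio is stated.

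**Step 1: reproduce E as a difference.**
- 10% of the quoted mean: 0.10 × 2.417 = 0.242 points; 0.2417 / 2.918 = 0.083 SD.
- 10% of the scale: 0.10 × 10 = 1 point; 1 / 2.918 = 0.34 SD.
- Base needed for 2.17 to be 10%: 2.17 / 0.10 = 21.7, more than twice the scale maximum. No VAS score, quoted or not, can be that base.
- As a difference, 2.17 is 2.17 / 2.417 = 90% of the reference mean.

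E is not reproduced.

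**Step 2: look for another route.** The only one found is 0.9 × 2.417 = 2.175, the mean left after a 10% fall. It gives 2.17 only by truncation. On that reading the difference is 2.417 − 2.175 = 0.242 points, and 0.70 SD has no basis.

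**Step 3: from E to 0.70.** 2.17 / 2.918 = 0.74, not 0.70. Obtaining 0.70 from 2.17 would need an SD of 2.17 / 0.70 = 3.10. With SD 2.918, 0.70 SD is 0.70 × 2.918 = 2.04 points.

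**Step 4: size of the gap.** 0.70 / 0.0828 = 8.5, or 0.70 / 0.343 = 2.0 on the 1-point reading.

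**Step 5: from 0.70 to the sample size.** By normal approximation, n per group = 2 × (1.645 + 0.842)² / 0.70² = 25.2, rounded up to 26. The noncentral t calculation gives 25.9, also 26, so 52 in total. With d = 0.74 it gives 24 per group, 48 in total. Two-sided at 0.70 it gives 34 per group. None of these is 28 in total.

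**Step 6: what 28 patients provide on that t-test.** Noncentral t, 26 df, noncentrality d × √(14/2), alpha 0.05, SD 2.918:

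| Difference | n per group for 80% power, one-sided (two-sided) | Power at 14 per group, one-sided (two-sided) |
|---|---|---|
| 0.242 points (0.083 SD) | 1,803 (2,289) | 7.6% (5.5%) |
| 1 point (0.34 SD) | 106 (135) | 22% (14%) |
| 2.04 points (0.70 SD) | 26 (34) | 56% (43%) |

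At 14 per group, 80% power is reached at 0.965 SD = 2.8 points one-sided, or 1.10 SD = 3.2 points two-sided.

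**Sensitivity to the SD.** With SD 3.10, power is 7.4% (5.4%) for 0.242 points and 21% (13%) for 1 point, and 80% power is reached at 3.0 (3.4) points. The conclusion does not change.

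**The case against.** **The 10% is a floor.** A trial may be powered for more than its minimum acceptable improvement, so a reader might infer that 0.70 SD is simply too large, or equally that 2.17 meets the criterion. The documents support neither. They do not say which figure was the target, so the ratios of 8.5 and 2 measure an inconsistency, not an excess. The inconsistency stands, because the sentence says E was obtained from the 10%.

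**E may be a target mean.** The match with 0.9 × 2.417 is close, and a reader might conclude that the remaining mean was entered as the difference. That is plausible but only an inference: neither 2.175 nor 0.74 matches the printed 2.17 and 0.70 exactly. If it is right, it explains E without rescuing 0.70.

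**28 might mean per group.** That would give about 83% one-sided power at 0.70 SD. The text describes 28 patients divided between two groups, which is a total.

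**The analysis is not a t-test.** This is correct. Section 8 specifies a repeated-measures ANOVA; the t-test belongs only to the sample-size calculation. A reader might infer that power for a 10% difference is also low under the ANOVA. That cannot be asserted, because no within-patient correlation is given. As an illustration only (not the model in section 8), take the baseline-adjusted mean of T1 to T3 under compound symmetry, with variance factor (1 + 2r)/3 − r². One-sided power for 1 point is then 48% at r = 0.7, 52% at 0.75 and 81% at 0.9.

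**Consequences are limited.** E enters no estimate or test in section 8, 0.70 is printed openly, and the patients have already been seen. This stands, and it confines the remedy to wording.

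**Separate matters.** The fall from 80% to 56% power comes wholly from 28 versus 52 patients and would remain if E were perfectly derived. The PBM versus placebo source is a further limitation, because no TENS versus PBM difference is specified. Neither adds weight to the point about E.

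**Conclusion.** The point holds in two separate parts.

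First, the 10% criterion does not support the effect used. On the quoted mean it implies 0.083 SD and on the full scale 0.34 SD, against 0.70 SD entered. No possible base on a 0-10 scale makes 2.17 a 10% improvement. This is plain arithmetic on printed figures; only the conversion to SD units assumes SD 2.918. Which figure the sponsor intended, and how 2.17 arose, remain open.

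Second, 28 patients in total does not follow from 0.70 SD with the stated alpha and power. This rests on a two-sample t-test; the 56% figure also assumes a 14:14 split.

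For interpretation, on the sample-size t-test a non-significant TENS versus PBM result should not be read as ruling out differences of the order of 10%. No power figure can be attached to the repeated-measures ANOVA from what the documents give.

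**What to change.** Stop presenting 10% and E = 2.17 as the basis of the sample size. The existing sentence can stay as the planning record, marked as not reproducible. The sponsor should state the base of the 10%, the derivation of E and the SD behind 0.70. Then add, labelled as recalculated:

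> The calculation used a standardised difference of 0.70 (about 2.04 points if SD = 2.918, taken from the placebo group of a PBM versus placebo study). With 28 patients (14 per group, 1:1 assumed), the two-sample t-test used for the sample-size calculation has about 56% power one-sided (43% two-sided) at alpha 0.05 for 0.70 SD, and 80% power only for about 0.97 SD (2.8 points) one-sided or 1.10 SD (3.2 points) two-sided. On that test, power is about 8% (5.5% two-sided) for 0.242 points and 22% (14%) for 1 point, so a non-significant TENS versus PBM difference should not be read as ruling out differences of the order of 10%. Power under the repeated-measures ANOVA of the analysis section depends on within-patient correlation, which was not specified.

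If another SD gave 0.70, name it and restate the values in points.

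The cost is wording only. Patients were seen "from April 2021 to February 2022", so the sample size and conduct stay as they are. The downside is that the stated power becomes less favourable than 80%, which follows from the error in the number of patients and not from E.

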## 6. Randomization

After sample size calculation and selection of the sample according to the inclusion criteria, the patients were randomized to one of the two treatments (TENS or PBM) using an allocation software (<https://www.graphpad.com/quickcalcs/randomize1/>). This program did not randomly choose a treatment for each patient but randomly shuffled a defined number of patients among a defined number of treatment slots.

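### Section 5's own inputs (two-mean t-test, d = 0.70, one-sided alpha 0.05, beta 0.20) need 26 patients per group, 52 in total, not 28; with 28 that test has about 56% power

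*Combined protocol and SAP*

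**What the plan says.** Section 5 (Sample size) names the method: the number was "calculated using a t-test for comparing the means of continuous variables". It then lists the other inputs and the result: "whose standardized effect size was 0.70 assuming a one-sided alpha error of 0.05 and a beta error of 0.20, resulting in 28 patients". The sentence ends "resulting in 28 patients divided into two intervention groups", so 28 is the trial total and not the number per arm. The section starts from a published comparison of PBM with sham laser, takes that study's placebo end-of-treatment VAS (mean 2.417, SD 2.918), and assumes that "acceptable improvement in the PBM group would be at least 10% after the intervention". It reports an effect value E of 2.17.

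Section 6 (Randomization) allocates patients to TENS or PBM and gives no allocation ratio. Section 8 (Statistical analysis) says, of VAS and salivary flow, "Two-factor ANOVA was used to analyze intergroup (TENS and PBM) and intragroup (repeated measures at T0, T1, T2 and T3) differences". Section 5 mentions no dropout allowance, within-patient correlation or gain from repeated measures.

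**The concern.** Every input to a standard two-sample calculation is printed beside its result, and the result does not follow from them. The stated total is little more than half of what the inputs require, so rounding cannot explain it.

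Section 4 makes VAS pain/burning the primary outcome, and Section 5 is the only justification of the trial's size. A reader who accepts a beta of 0.20 will think that a 0.70 SD difference between TENS and PBM would probably have been found. A non-significant result could then be taken as evidence that the two treatments perform alike, when the test named in Section 5 would miss such a difference nearly half the time.

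**Working it through.** **Inputs, all from Section 5:** t-test comparing two means; d = 0.70; one-sided alpha 0.05; beta 0.20 (power 0.80); total N = 28 in two groups. **Assumption:** 1:1 allocation (14/14), because the documents give no ratio.

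**1. Trying to reproduce 28.** The normal approximation for two independent means is

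n per group = 2 × (z₀.₉₅ + z₀.₈₀)² / d² = 2 × (1.645 + 0.842)² / 0.49 = 25.2, rounded up to 26.

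The exact calculation uses the noncentral t distribution with n₁ + n₂ − 2 degrees of freedom and noncentrality d × √(n₁n₂/(n₁ + n₂)):

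| Per group | Noncentrality | One-sided 5% critical value | Power |
|---|---|---|---|
| 25 | 0.70 × √12.5 = 2.475 | 1.677 | 0.787 |
| 26 | 0.70 × √13 = 2.524 | 1.676 | 0.801 |

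Both routes give 26 per group, 52 in total. The stated 28 is not reproduced.

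**2. Power that 28 patients give.** At 14/14 the noncentrality is 0.70 × √7 = 1.852, on 26 degrees of freedom with critical value 1.706. One-sided power is 0.563, so the type II error is 1 − 0.563 = 0.437. Two-sided at 5%, power is 0.430. A simulation of 200,000 trials per case gave 0.563 and 0.430 at 14 per group, and 0.802 one-sided at 26 per group. Unequal splits lower the one-sided power: 0.561 at 13/15, 0.556 at 12/16 and 0.533 at 10/18.

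**3. Other readings that might yield 28.**

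| Reading | Result |
|---|---|
| 28 per group, one-sided | power 0.827 |
| Paired or one-sample t-test, d = 0.70, one-sided | power 0.768 at n = 13, 0.798 at 14, 0.824 at 15 |
| Two groups, two-sided 5% | 34 per group, 68 in total |
| Two groups, one-sided, d = E/SD = 2.17/2.918 = 0.74 | 24 per group, 48 in total |

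The first contradicts the wording, which divides the 28 between the arms. The second comes very close to 14 per group, but it concerns change within one group. The last two move the total further from 28 or leave it far above. E is not otherwise used as a difference here, because 0.9 × 2.417 = 2.175 suggests that it is a target mean.

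**4. What 14/14 can detect.** The single-visit, unadjusted t-test has 80% power at d = 0.965 one-sided and d = 1.100 two-sided. At the SD quoted in Section 5 these are 0.965 × 2.918 = 2.82 and 1.100 × 2.918 = 3.21 VAS points, against 0.70 × 2.918 = 2.04 points for the planned effect. The 95% confidence interval half-width for the group difference is 2.056 × 2.918 × √(2/14) = 2.27 points. The point values are illustrative: the SD is that of an external placebo arm, and Section 5 does not show that 0.70 was derived from it.

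**The case against.** The strongest defence is that Section 5 never says the samples are independent and never ties 0.70 to TENS versus PBM. It speaks of improvement within the PBM group and draws on a PBM-versus-placebo study. Read as a within-group test, 14 patients per arm give 79.8% power and two arms make 28. On that view the arithmetic is nearly right and the wrong test was sized. This may well be how the number arose, but it is an inference. Strict rounding would still give 15 per arm, and the calculation would then say nothing about the comparison that Section 6 randomizes for and Section 8 tests. Section 5 needs correcting on either reading.

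A second argument is that Section 8 plans a repeated-measures ANOVA, so a single-visit t-test understates the power. This could be so. As an illustration, baseline adjustment with an assumed correlation of 0.7 would give about 81% one-sided power at 14/14. The documents state no correlation, and Section 5 claims no such gain, so this does not support the stated number. What stands is a limit on the claim: 56% and 44% describe the t-test that Section 5 names, not the planned ANOVA.

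It can also be said that the study period ended in February 2022 and that a confidence interval shows the precision directly. That bears on the remedy, which is kept to wording. It does not make the stated beta correct.

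**Conclusion.** The concern holds. Read as an independent two-sample t-test, which is what a comparison of two randomized arms calls for, Section 5's inputs require 52 patients and not 28. At 28 that test, at a single visit and without adjustment, has about 56% one-sided power, so the stated beta of 0.20 is really about 0.44.

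The required number does not depend on how the 28 were split. The power figure assumes 14/14, which is the most favourable split. Both are conditional on d = 0.70 and do not endorse that value. The power of the Section 8 ANOVA is unknown. Because Section 5 is the sole justification of the trial's size for its primary outcome, the statement must be corrected. Confidence is high.

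**What to change.** Add a dated, disclosed correction to Section 5 and leave the existing text visible. Suggested wording:

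> At d = 0.70 and one-sided alpha 0.05, a two-group t-test needs 26 per group (52 in total) for 80% power. With 28 patients (14 per group, if allocation was 1:1), the power of a single-visit, unadjusted t-test is about 56% one-sided (about 43% two-sided at 5%). The difference that this test can detect with 80% power is d = 0.97 one-sided (about 2.8 VAS points at the stated SD of 2.918) or d = 1.10 two-sided (about 3.2 points). The power of the repeated-measures ANOVA in Section 8 was not calculated. The required number and the power are conditional on d = 0.70 and do not endorse it.

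If the 28 came from a within-group formula, the correction should say so. Report the TENS minus PBM difference in VAS with its 95% confidence interval, naming the visit and stating whether it is adjusted for baseline, so that a non-significant result is read against its precision.

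The cost is wording only. No patients are added and the planned analysis does not change. The one downside is a less favourable stated power.

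### The standardised effect of 0.70 does not follow from the effect and SD given in Section 5, and neither 0.70 nor the 0.744 they imply gives 80% power with 28 patients

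*Combined protocol and SAP*

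**What the plan says.** All the planning figures are in Section 5 (Sample size) of the combined protocol and SAP.

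- **Source data.** A cited trial of PBM against laser-off placebo supplies the post-treatment VAS score of its placebo arm: mean 2.417, SD 2.918.
- **Target.** The plan takes the view that "acceptable improvement in the PBM group would be at least 10% after the intervention".
- **Effect.** The effect derived from that target is E = 2.17.
- **Calculation.** The plan compares two means by t-test at a 5% one-sided level with 80% power. The effect entered is described by the phrase "whose standardized effect size was 0.70".
- **Result.** 28 patients in total over two groups. The allocation ratio is not stated.

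Section 5 does not say how 0.70 was obtained, which SD was the divisor, or how figures were rounded.

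**The concern.** For a t-test comparing two means, the standardised effect is the difference in means divided by the SD. Section 5 offers one candidate for each, and their ratio is not the value it then uses. A reader cannot tell whether the trial was planned around 2.17 points on the VAS, around the 2.04 points that 0.70 implies with the stated SD, or around a different SD.

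The standardised effect, with alpha, sidedness, power and allocation, determines the sample size. If the chain from effect to SD to standardised effect to n cannot be followed, the claim of 80% power for the primary outcome cannot be checked. When it is followed with either candidate value, the claim fails. That affects how a non-significant TENS versus PBM comparison should be read.

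**Working it through.** **Inputs (all from Section 5).** Placebo mean 2.417; SD 2.918; improvement 10%; E = 2.17; standardised effect d = 0.70; one-sided alpha 0.05; beta 0.20; total 28. Assumption: 1:1 allocation, so 14 per group.

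**Step 1. Can 0.70 be reproduced?**

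- d = E/SD = 2.17/2.918 = 0.744.
- Allowing for rounding of E (2.165 to 2.175), the ratio runs from 0.742 to 0.745. This does not reach 0.705, the top of the range that would print as 0.70.
- To one decimal place, 0.744 is 0.7.
- An exact 0.70 needs either an effect of 0.70 × 2.918 = 2.04 or an SD of 2.17/0.70 = 3.10. Neither figure is in the document.

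**Step 2. Can 28 be reproduced?** The normal approximation per group is n = 2(z₀.₉₅ + z₀.₈₀)²/d², with z values 1.645 and 0.842.

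- d = 0.70: n = 2 × 2.486²/0.49 = 25.2, so 26. The exact noncentral t gives 25.94, so 26 per group and 52 in total.
- d = 0.744: n = 22.4, so 23. The exact t gives 23.07, so 24 per group and 48 in total.

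Neither gives 28 in total.

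**Step 3. Power with 14 per group.** Exact t, 26 degrees of freedom, noncentrality d × √(14/2).

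| d | One-sided 5% | Two-sided 5% |
|---|---|---|
| 0.70 | 56.3% | 43.0% |
| 0.744 | 60.7% | 47.4% |

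For 80% one-sided power, d must be about 0.97 by the exact t (0.94 by the normal approximation).

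**Step 4. Other readings of 28.**

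- As a per-group figure, 28 is close to the 26 needed at d = 0.70 and would give about 83% one-sided power, but the text divides 28 between the two groups.
- A one-sample or paired calculation at d = 0.70 needs 13 (normal) to 15 (exact t) in each group, or 26 to 30 over two. This brackets 28 but is not the between-group comparison that Section 5 implies.

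**Step 5. What is E?**

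- 0.9 × 2.417 = 2.175, which agrees with 2.17. So E matches the score remaining after a 10% reduction.
- The 10% reduction itself is 0.1 × 2.417 = 0.24 points, and 0.2417/2.918 = 0.083 SD.
- At d = 0.083, 80% one-sided power needs about 1,803 per group, and 14 per group gives about 7.6%.

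**The case against.** The strongest reply has four parts.

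1. **The text never equates 0.70 with 2.17/2.918.** The SD given belongs to one arm of the cited study. A two-sample calculation could use a pooled SD, and one near 3.10 would give 0.70. This stands. The cited study is not available here, so a reader who infers a proven arithmetic error goes beyond the document. What it supports is that the derivation is not shown and does not follow from the figures that are.

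2. **Rounding could explain the gap.** This stands as a possibility. Against it, 0.70 is printed to two decimals, beside figures given to two or three, and no coarser rounding is mentioned.

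3. **The gap did no harm.** This also stands for the gap alone. Using 0.70 in place of 0.744 raises the requirement from 48 to 52 patients. A reader might infer that the mismatch made the trial too small, but it works in the other direction. The shortfall comes from the 28, whichever value is used.

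4. **If E is not a difference, neither 0.70 nor 0.744 means anything.** This is right. It rules out the tempting reading that the step is wrong however E was derived, and with it the obvious repair of writing 0.74. That repair would make the paragraph look consistent while still treating a remaining score as a difference.

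The reply does not rescue the power claim. No reading of the stated inputs as a two-group comparison of 28 patients in total gives 80%.

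**Conclusion.** The point holds in a limited form. The mismatch between 0.70 and 0.744 is a gap in the reported derivation: about 6%, cautious for n, and possibly due to rounding or an unstated SD. By itself it would be a minor note.

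What makes it worth correcting is that the 80% power claim is unsupported at either value. With 28 patients, the power is about 56% to 61% one-sided, or 43% to 47% two-sided. The two-sided figures are relevant because the ANOVA group and interaction tests in Section 8 are not directional. These figures assume 1:1 allocation and a simple two-sample t-test, as in Section 5. They do not allow for any precision gained from repeated measures, for which the plan gives no correlation. They also treat 0.70 or 0.744 as a true between-group difference, which Section 5 does not establish; at its literal 10% improvement, power would be far lower.

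**What to change.** Rewrite the Section 5 calculation as follows.

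- State the between-group difference in VAS points, the SD and its source, and the standardised effect as their ratio, so that only one consistent set remains.
- Do not simply change 0.70 to 0.74. First say whether 2.17 was meant as a difference or as the expected remaining score, then compute the standardised effect from the difference.
- If 0.70 is kept, state the difference (2.04 with SD 2.918) or the SD (3.10, with its source) that produces it.
- Replace the 80% claim by the power that 28 patients provide at the stated effect: about 56% one-sided at 0.70, with 14 per group. Give the two-sided figure (43%) beside it and state the allocation ratio.

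The cost is a short rewrite, one recalculation and a less favourable stated power. Because Section 1 describes the trial as already conducted, this corrects the planning statement and calls for no further patients.
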